## **Secondary outcomes**

1. Trend over time of quantitative viral load at Day 7, 14 and Day 30 as measured by quantitative, digital droplet PCR.
2. Time to clinical resolution (for symptomatic patients).
3. Proportion of patients with virological clearance at day 14 and 30
4. Rate of hospitalization.
5. COVID-19 Severity Score at Day 14 and Day 30

## **Statistical design and sample size**

The statistical study design is conceived in 2 steps.

The patients will be randomised to I\_600 + placebo or I\_1200 or placebo with an allocation ratio=1 :1 :1.

### **Step 1:**

#### Safety analysis

After randomisation of the first 60 evaluable patients (20 per arm) a first analysis will be performed on the 2 experimental treatments for safety purpose. Safety endpoint will be the occurrence of a SADR. Definitions are reported in the paragraph «Definition and reporting of adverse events»

A'Hern single stage design (A'Hern 2001) will be adopted. For each experimental arm, the null hypothesis that the true toxicity rate is 30% will be tested against a one-sided alternative. The null hypothesis will be rejected if  $\leq 4$  SADRs are observed in 20 patients. This design yields a type I error rate of 10% and power of 80% when the true toxicity rate is 5%.

If  $\geq 5$  SADRs are observed in one of the experimental arms, the allocation of patients to that arm will be interrupted and the study will continue for efficacy analysis only for the control arm and the other treatment arm. In case that  $\geq 5$  SADRs will be experienced in both arms the study will be stopped.

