### ***Primary outcomes***

1. Number of serious adverse drug reaction (SADR).
2. Quantitative viral load at Day 7 as measured by quantitative, digital droplet PCR.

NB: The primary outcome no.2., as well as all secondary outcomes, will be measured only if the number of SADR is less than 4 in at least one of the treatment arms.

---

 1 is "no limitation of activities", 2 is "limitation of activities", 3 is "hospitalized, no oxygen therapy", 4 is "hospitalized, oxygen by mask or nasal prongs", 5 is "non-invasive ventilation or high-flow oxygen", 6 is "intubation and mechanical ventilation", 7 is "ventilation + additional organ support - pressors, RRT (renal replacement therapy), ECMO (extracorporeal membrane oxygenation)", and 8 is "death".

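### The Step 1 safety rule does not have the error rates printed for it: 4 or fewer SADRs in 20 patients gives a type I error of 23.8%, not 10%, and power of 99.7%, not 80%

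*Protocol*

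**What the plan says.** Under *Statistical design and sample size*, Step 1, the protocol says "A'Hern single stage design (A'Hern 2001) will be adopted". The test is carried out separately in the two ivermectin arms, and its hypotheses are set out as follows: "the null hypothesis that the true toxicity rate is 30% will be tested against a one-sided alternative". The timing and size are also given: "After randomisation of the first 60 evaluable patients (20 per arm) a first analysis will be performed on the 2 experimental treatments for safety purpose". The null is rejected when 4 or fewer "SADRs are observed in 20 patients". The complement is stated as well: 5 or more SADRs in one experimental arm stops allocation to that arm, and 5 or more in both stops the study. The operating characteristics follow: "This design yields a type I error rate of 10% and power of 80% when the true toxicity rate is 5"%.

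The *Primary outcomes* section lists the number of SADRs as the first primary outcome. Its note says that viral load and all secondary outcomes will be "measured only if the number of SADR is less than 4 in at least one of the treatment arms".

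**The concern.** Every input to the two printed error rates is given in the same paragraph, so they can be checked directly, and they do not look compatible with the rule. Under a 30% rate the expected count in 20 patients is 6, so a result of 4 or fewer is not rare. Under a 5% rate the expected count is 1, so a result of 4 or fewer is almost certain.

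The rule carries weight. It answers the first primary objective (safety of the two dosages) and determines which arms enter the interim efficacy and futility analyses and the final comparison. *Rationale and background* says the second phase begins only after safety has been confirmed. The type I error here is the probability of declaring safe an arm whose true SADR rate is 30%. An ethics committee or regulator reading the protocol is told that this probability is 10%.

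**Working it through.** **Inputs** (Step 1, Safety analysis): n = 20 per experimental arm; null rate p0 = 0.30, one-sided; alternative rate p1 = 0.05; reject the null if X ≤ 4, where X is the number of patients with a SADR.

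**Formula.** An exact single-stage design uses the binomial distribution: P(X ≤ c) = Σ (k = 0 to c) C(20, k) p^k (1 − p)^(20 − k). At p0 this is the type I error; at p1 it is the power.

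**Attempt to reproduce the stated 10% and 80% with c = 4:**

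- p = 0.30: 0.0008 + 0.0068 + 0.0278 + 0.0716 + 0.1304, total **0.2375** from unrounded terms (stated 0.10).
- p = 0.05: 0.3585 + 0.3774 + 0.1887 + 0.0596 + 0.0133, total **0.9974** from unrounded terms (stated 0.80).

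Neither figure is reproduced.

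**Other cut-offs at n = 20:**

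| Null rejected if SADRs | Type I error (true rate 30%) | Power (true rate 5%) |
|---|---|---|
| ≤ 1 | 0.8% | 73.6% |
| ≤ 2 | 3.5% | 92.5% |
| ≤ 3 | 10.7% | 98.4% |
| ≤ 4 (Step 1) | 23.8% | 99.7% |

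No row gives 10% with 80%. The printed 10% is close only to the row for 3 or fewer, which is the threshold in *Primary outcomes*. The printed 80% matches no row.

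**Other readings tried:**

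- Normal approximation, c = 4: type I error 16.5% without and 23.2% with continuity correction; power above 99.8% either way.
- Hypotheses reversed (null 5%, reject at 5 or more): type I error 0.26%, power at 30% of 76.2%. Rejecting at 4 or more: 1.6% and 89.3%.
- Cut-off held at ≤ 4, n varied: the type I error first falls to 10% or below at n = 25 (9.05%).
- Smallest exact design for 30% against 5% with type I error at most 10% and power at least 80%: n = 12 with at most 1 event (8.5% and 88.2%).

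None returns the printed pair for 20 patients.

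**What the rule does at the margin.** At exactly 4 of 20 the null is rejected although the one-sided p-value is 0.24 and the exact one-sided 90% upper limit for the SADR rate is 36.1%, so 30% is not excluded. At 3 of 20 the p-value is 0.107, just above 10%. With 0 to 2 events, 30% is excluded at the 10% level.

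**Where 80% does apply.** Solving P(X ≤ 4) = 0.80 at n = 20 gives a true rate of 15.8%, not 5%.

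**Illustration for two arms.** If both doses had a 30% rate and the arms are independent, at least one would pass with probability 1 − (1 − 0.2375)² = 41.9%, against 1 − 0.9² = 19.0% if the per-arm error were 10%. The protocol claims no joint error rate, so this only shows scale.

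**The case against.** The strongest reply is that 10% and 80% are nominal design limits rather than achieved values. That answers the power figure: 99.7% satisfies a floor of 80%, and a low-toxicity arm is not dropped more often than promised. It does not answer the type I error, because 23.8% breaks a ceiling of 10%. The sentence also presents both figures as what the design delivers.

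A second reply is that the cut-off is a slip for 3 or fewer, as in *Primary outcomes*. This may explain the 10%, but that cut-off gives 10.7% and 98.4%, so the printed pair would still be wrong. Step 1 also states its threshold consistently from both sides, 4 or fewer to pass and 5 or more to stop.

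Third, the counting unit matters. Step 1 and *Primary outcomes* refer to numbers of SADRs, while *Analysis of the primary outcome* counts patients with at least one. If events were counted and some patients had several, the chance of passing at a 30% patient-level rate would be below 23.8%. This is a fair caveat, but the Step 1 endpoint is the occurrence of a SADR, and the binomial design requires the patient-level count.

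Finally, Step 1 is not the only safeguard. *End of Study* and *Procedure for the conclusion of the trial* allow stopping for severe or unexpectedly serious or frequent adverse events, and SAEs are reported within 24 hours. These soften the practical consequence, but they carry no error rate and do not correct the printed one.

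**Conclusion.** The statement is wrong as written. For the rule in Step 1 the type I error is 23.8% against a stated 10%, and the power at a 5% rate is 99.7% against a stated 80%. The first error is the material one: the probability of passing an arm with a true 30% SADR rate is understated by more than half, on a decision rule for a primary objective.

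The cut-off also conflicts with *Primary outcomes*. If neither experimental arm has fewer than 4 SADRs and at least one has exactly 4, Step 1 sends that arm on to the efficacy analysis, while *Primary outcomes* says the efficacy outcomes are not measured.

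The figures assume independent patients, 20 evaluable patients per arm, and each patient counted at most once.

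**What to change.** Make the cut-off and its error rates belong together, and use the same cut-off in Step 1 and *Primary outcomes*.

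- If 4 or fewer is kept, print a type I error of 23.8% and power of 99.7% at a 5% rate, and change the note in *Primary outcomes* to match.
- If a type I error of about 10% is the requirement, print the cut-off chosen to meet it with its exact type I error and power, and change both sentences in Step 1 that refer to 5 or more SADRs. At 20 patients the available type I errors step from 3.5% to 10.7% to 23.8%, so none equals 10%.
- Print the exact table for cut-offs of ≤ 2, ≤ 3 and ≤ 4 (3.5%/92.5%, 10.7%/98.4%, 23.8%/99.7%) so that the choice is visible.
- State that the count is of patients with at least one SADR, as in *Analysis of the primary outcome*.

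Which limit is acceptable is for the sponsor and its safety reviewers. The cost is a few sentences of protocol text and no additional patients. If the present cut-off stays, the published false-safe rate becomes less favourable; if it changes, the decision rule itself is amended.

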## **Analysis of the primary outcome**

The proportion of patients in each experimental group experiencing at least one SADR will be described by means of frequency and percentages.

The mean of the differences in viral load decline from baseline to 7 days between each experimental group and the control group will be described by standard summary measures for continuous data and compared by mean of Student T test or the equivalent non parametric method (according to the Barlett's test for homogeneity of variances).

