## **PROCEDURE FOR THE CONCLUSION OF THE TRIAL**

The trial will be concluded when the expected number of patients to be enrolled will be reached, or before if unexpectedly serious/frequent adverse events should be recorded in one or in both the treatment groups. In case this only happens in the arm b) of the treatment group, this arm will be immediately stopped and the trial will continue with the comparator group and the arm a) of the treatment group.

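### The Step 1 safety rule (4 or fewer SADRs in 20) has a type I error of 23.8%, not the stated 10%, and the Primary outcomes section uses a different cut-off

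*Protocol*

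**What the plan says.** The safety rule is in the Protocol, Statistical design and sample size, Step 1, Safety analysis. On timing it says: "After randomisation of the first 60 evaluable patients (20 per arm) a first analysis will be performed". On method: "A'Hern single stage design (A'Hern 2001) will be adopted". For each experimental arm the null hypothesis is a true toxicity rate of 30%, tested one-sided, and it is rejected at 4 or fewer SADRs in 20 patients. The stated properties are: "This design yields a type I error rate of 10% and power of 80% when the true toxicity rate is 5" (per cent).

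The stopping sentences mirror the cut-off. If 5 or more "SADRs are observed in one of the experimental arms, the allocation of patients to that arm will be interrupted", and if 5 or more "SADRs will be experienced in both arms the study will be stopped".

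The Primary outcomes section sets a different condition. Viral load at Day 7 and all secondary outcomes "will be measured only if the number of SADR is less than 4 in at least one of the treatment arms".

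**The concern.** The quoted error rates do not look right for the rule as written. With 20 patients and a true rate of 30%, 6 SADRs are expected (20 × 0.30). Seeing 4 or fewer is then too common for a 10% error rate.

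Safety is the first primary objective, and this is the only quantified safety gate to Step 2. Readers who rely on the stated 10%, including ethics committees and safety reviewers, would be misled about how often an arm at the unacceptable rate goes forward.

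The second problem is the boundary. An arm with exactly 4 SADRs passes under Step 1 but does not meet the Primary outcomes condition. If that is the better of the two experimental arms, one section continues to efficacy and the other says efficacy is not measured.

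**Working it through.** **Inputs**, all from Step 1, Safety analysis, unless noted:
- 20 patients per arm
- null rate 30%, alternative rate 5%
- pass at X ≤ 4, drop at X ≥ 5, where X is the number of patients with a SADR
- stated type I error 10%, stated power 80%
- Primary outcomes section: fewer than 4, that is X ≤ 3

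**Attempt to reproduce the stated figures.** The design named is an exact single-stage design, so the exact binomial applies.

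Type I error = P(X ≤ 4 | n = 20, p = 0.30) = 0.0008 + 0.0068 + 0.0278 + 0.0716 + 0.1304 = 0.2375 (to rounding), or **23.8%**.

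Power = P(X ≤ 4 | n = 20, p = 0.05) = 0.9974, or **99.7%**.

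The non-toxicity scale (16 or more of 20 patients free of SADR, 70% against 95%) gives the same two values. Neither stated figure is reproduced.

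**Other routes to 10%, all unsuccessful:**
- Normal approximation: mean 6, variance 20 × 0.3 × 0.7 = 4.2. Without continuity correction, Φ((4 − 6)/√4.2) = 16.5%. With it, Φ((4.5 − 6)/√4.2) = 23.2%.
- Hypotheses reversed (null 5%, reject at 5 or more): type I error 0.26%, power at 30% of 76.2%.
- Cut-off 4 with more patients: 11.1% at n = 24 and 9.0% at n = 25. The error first falls to 10% or below at 25 per arm.

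**Cut-offs at n = 20:**

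| Pass if | Type I error at 30% | Power at 5% | Chance of stopping an arm whose true rate is 5% |
|---|---|---|---|
| 4 or fewer | 23.8% | 99.7% | 0.3% |
| 3 or fewer | 10.7% | 98.4% | 1.6% |
| 2 or fewer | 3.5% | 92.5% | 7.5% |

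Under the written rule an arm with a true rate of 25% passes 41.5% of the time, and one at 20% passes 63.0% of the time.

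**How often the two sections conflict.** I read the treatment arms in the Primary outcomes condition as the two experimental arms, take it to refer to the same 20-patient look, and treat the arms as independent. The condition is on the trial as a whole, so the conflict arises only when neither arm has 3 or fewer and at least one has exactly 4:

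P(conflict) = P(X₁ ≥ 4)P(X₂ ≥ 4) − P(X₁ ≥ 5)P(X₂ ≥ 5)

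- Both rates 30%: 0.8929² − 0.7625² = 0.7973 − 0.5814 = 0.2159, or 21.6%.
- Rates 30% and 5%: 0.8929 × 0.0159 − 0.7625 × 0.0026 = 0.0122, or 1.2%.
- Both rates 5%: 0.0159² − 0.0026² = 0.00025, or 0.02%.

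**The case against.** Several points can be made for the plan.

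- *Power.* Exact designs move in steps, so 80% may be meant as a minimum, and 99.7% meets it. This stands: the power figure is loose but harmless. The same reading cannot rescue the type I error, because 10% is not a ceiling if the true value is 23.8%.
- *Other safeguards.* The section on concluding the trial allows an end once the planned number is enrolled, "or before if unexpectedly serious/frequent adverse events should be recorded in one or in both the treatment groups". The End of Study section also allows recruitment to stop for severe adverse events or an unfavourable Step 1 safety profile in both arms, and SAEs must be reported within 24 hours. So a toxic arm is not held back by this rule alone. None of these provisions gives a threshold, however, and none corrects the stated error rate. The interim efficacy and futility rules are numeric but do not address safety.
- *Plausibility.* A SADR rate near 30% would be extreme in patients with mild infection, and the conflict is very rare if both arms are safe. That is true, but 30% is the rate the Protocol itself chose as its null, and the rule matters most when an arm is not safe.
- *A misprint.* A cut-off of 3 or fewer gives 10.7%, the closest value to 10%, so Step 1 may contain an off-by-one slip. That is inference. The cut-off of 4 is consistent with both stopping sentences at 5 or more, so it is not an isolated wrong symbol.

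Leaving the matter to a later analysis plan does not help: the Protocol states a wrong figure and two inconsistent thresholds.

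**Conclusion.** The Protocol is wrong as written on both counts. The Step 1 rule has a type I error of 23.8% per arm, more than twice the stated 10%. This rests only on the Protocol's own inputs and the exact binomial distribution. The cut-offs in Step 1 and in the Primary outcomes section contradict each other when the better experimental arm has exactly 4 SADRs. The probability of that is 21.6% if both arms are at the unacceptable rate and 0.02% if both are at 5%, under the assumptions of independent arms and the same look. The rule is the only quantified safety gate to Step 2 and serves the first primary objective, so it must be corrected. The efficacy sample size and error rates are not affected.

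**What to change.** Use one cut-off in Step 1 and in the Primary outcomes section, and state its exact type I error and power. The choice of cut-off belongs to the sponsor and the safety reviewers.

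- **Keep 4 or fewer:** replace 10% and 80% in Step 1 by 23.8% and 99.7%, and change the Primary outcomes condition to fewer than 5. The cost is a less favourable stated error rate.
- **Move to 3 or fewer:** state 10.7% and 98.4%, change both stopping sentences in Step 1 to 4 or more, and leave the Primary outcomes condition at fewer than 4. The chance of stopping an arm whose true rate is 5% rises from 0.3% to 1.6%.
- **Move to 2 or fewer:** state 3.5% and 92.5%, change the stopping sentences to 3 or more and the Primary outcomes condition to fewer than 3. Of the three, only this one keeps the type I error at or below 10%. The chance of stopping an arm at 5% rises to 7.5%.

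None of these needs extra patients. Keeping a cut-off of 4 with a type I error at or below 10% would instead need the look at 25 per arm (9.0%, power 99.3%).

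As a minor clarification, word the count in both places as patients with at least one SADR. The Analysis of the primary outcome section already does so: "The proportion of patients in each experimental group experiencing at least one SADR". Any of these changes is a protocol amendment, which the Ethical aspects section requires to be approved by the Ethics Committees.

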## **STUDY DESIGN**

This is a multicentre, prospective, randomized, double-blind, adaptive phase II dose finding study.

Patients meeting the inclusion criteria will be asked to participate to the study and randomized in a 1:1:1 ratio to either:

- Placebo arm (arm A): placebo will be identical in appearance to ivermectin in order to preserve blinding and will be administered p.o. at empty stomach with water once daily, for 5 days

- Intervention arms: a) Ivermectin, single dose 600 µg/kg, for 5 days (I\_600) and placebo (arm B) ; b) Ivermectin, single dose 1200 µg/kg, for 5 days (I\_1200) (arm C) ); these drugs will be administered p.o. once daily, for 5 days.

In arm A and B, the number of placebo tablets to be administered will be calculated by the study dedicated pharmacist considering the number of tablets that should be taken in case a patient with the same weight is assigned to arm C.

[figure not shown]
Patients will be randomized by a centralized computer system. At randomization a treatment ID is assigned to the patient. Once a treatment ID is assigned this must not be re-assigned even in cases of errors.

Enrolled subjects will be identified by a unique subject number (patient code) that will remain consistent for the duration of the study.

Patients will be recruited at the emergency room of hospitals, and/or among asymptomatic hospital workers found positive for SARS-CoV-2 at routine screening and/or in outpatient ambulatory settings, and/or at home, if not meeting the clinical criteria for hospitalization, according to the routine procedure of each participating site. The expected duration of subjects inclusion in the study is of 3 months, or until the planned number of subjects to be enrolled will be reached.

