Each experimental arm passing the step 1, will be compared with control arm at a statistical significant level of 0.025, one side. In this way, in case that both arms are considered for the efficacy comparison, the statistical significant level will be set to 0.025, 1 side, in order to preserve an overall family wise error of 0.05. Primary endpoint will be the difference in viral load decline from baseline to 7 days. Viral load will be measured as  $\log_{10}$  of genome copies per mL, ascertained by Digital Droplet quantitative PCR (DD-PCR). In order to calculate the sample size, we refer to data recently published on Lancet Inf. Dis. (To 2020), showing that in a population with mild disease presentation, the difference in mean viral load from baseline to 7 days is 1.05  $\log_{10}$  copies per mL (from 0.77 to 1.33  $\log_{10}$  copies, calculated from the slope and its 95%CI), with an estimated SD=0.69  $\log_{10}$  copies per mL. The desired difference in decrease between each experimental group and control is at least 0.47  $\log_{10}$  copies per mL in order to detect an effect size  $\Delta = 0.68$  (considered to be of moderate-large magnitude according to Cohen 1988). According to these hypotheses, with 34 pts per arm the study has a power=80% to detect a statistically significant difference between the experimental vs. control arm, at 0.025 alpha level, one side.

Therefore, if both experimental treatments will be compared with control group, the total number of patients to be analyzed will be 102. Considering a potential 20% loss to follow-up, it is planned to enroll 129 patients.

If only one experimental group is compared with control arm, the total number of evaluable patients will be 84 (105 to be enrolled).

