### ***End of Study***

The end of the study is defined as the last follow-up visit of the last patient. The Ethics Committees will be notified within 90 days of the end of the study.

Recruitment will be stopped once the required number of patients is reached or in case of (unexpected and most unlikely) severe adverse events in the treatment arm or if the analysis of the first step will show an unfavorable safety profile of both experimental arms.

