## ***Pharmacokinetics study***

Exploratory endpoint:

Association between plasma drug concentration and clinical endpoints

Plasma ivermectin concentration

The measurement of the drug concentrations in the plasma is included in the project, as ancillary study, to assess inter-individual differences in drug bioavailability which can underlie either no or poor efficacy (insufficient blood concentrations) or adverse events (too high blood concentrations). In fact, a high variability in absorption has been described (Guzzo et al., 2002).

In order to avoid too much distress to the patients, together with considerations on feasibility, blood samples will be collected in a subset of patients ( $\geq 10$  per dose), at three time-points (just before, four and 72 hours after the fifth dose) chosen according to pharmacokinetic considerations (see below).

Ivermectin will be administered orally at doses of 600 or 1200 ug/kg, once daily for five days.

Following oral administration of ivermectin in humans, the peak plasma concentrations ( $t_{max}$ ) are observed at approximately four hours after dosing, and the apparent half-life is approximately 18 hours (Guzzo et al., 2002). With this PK profile, repeated daily administrations are expected to result in some accumulation of the drug. For these reasons and for feasibility considerations, blood levels of ivermectin will be measured at the following three time points: just before, and 4 and 48 hours after, the fifth dose. These data will inform on the maximal drug levels and the drug accumulation following repeated doses, on the inter-individual variability and, possibly, on association between blood drug dose and clinical endpoints.

Ivermectin will be measured in plasma samples by HPLC-MS/MS at the laboratory of the IRCCS-Sacro Cuore Don Calabria hospital. The method of analysis for ivermectin concentrations in plasma has already been validated according to the EMA guidelines.

Blood samples are withdrawn at protocol-defined times in 2x7 mL EDTA tubes (lavender top). Tubes are gently inverted for 6-8 times. The sample collection date and time must be entered.

The tubes are centrifuged at 2000 g for 10 minutes at room temperature within 2 hours from withdrawal. The supernatant is splitted in 1.0 ml aliquots in 2.0 mL polypropylene tubes. Aliquots (analysis samples) are then stored at  $-20^{\circ}\text{C}$  (or lower T) until analysis.

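### If 600 µg/kg alone fails the Step 1 safety rule, randomisation to 1200 µg/kg continues automatically; it should pause for a documented safety review, and the closing sections should cover this case

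*Protocol*

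**What the plan says.** Three parts of the protocol govern what follows a safety failure.

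- **Statistical design and sample size, Step 1, Safety analysis.** Each ivermectin arm is judged on its own 20 patients. Four or fewer SADRs pass; five or more close the arm, and then "the study will continue for efficacy analysis only for the control arm and the other treatment arm". The study stops only if both arms reach five. The rule is the same whichever dose fails.
- **Procedure for the conclusion of the trial.** The trial ends when enrolment is complete, "or before if unexpectedly serious/frequent adverse events should be recorded in one or in both the treatment groups". One continuation is written: "In case this only happens in the arm b) of the treatment group, this arm will be immediately stopped", and the comparator and arm a) go on. The Study Design section lists the intervention arms as a) 600 µg/kg and "b) Ivermectin, single dose 1200" µg/kg.
- **End of Study.** Recruitment stops when the target is reached, for severe adverse events in the treatment arm (no criterion given), "or if the analysis of the first step will show an unfavorable safety profile of both experimental arms".

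None of these sections provides a pause, or a review of 1200, when 600 alone fails.

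**The concern.** The two arms give the same drug on the same five-day schedule, one at twice the daily dose of the other. If the lower dose produces enough serious reactions to be closed, that is information about the higher dose as well. Step 1 does not use it: 1200 continues on its own count.

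Nothing in the protocol suggests that 1200 is the safer dose. The Rationale predicts a first-dose peak of 230 ng/mL at 1200 and cites measured peaks of 105-119 ng/mL after 600. Appendix 1 says that differences in drug bioavailability are something "which can underlie either no or poor efficacy (insufficient blood concentrations) or adverse events (too high blood concentrations"). The Rationale also says that the second phase will begin only once safety has been confirmed.

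At stake is the exposure of a further 12 to 22 evaluable patients to the doubled dose, with no required look at what closed the lower one. The section on concluding the trial does not help. It foresees only the higher dose being dropped, so a team facing the opposite result has a rule in one place and silence, or arguably a different answer, in another.

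**Working it through.** **1. Which dose is arm b)?** Capital arm B is 600, whereas lower-case b) in the Study Design list is 1200. If b) in the concluding section meant capital B, then a) would be capital A, which is placebo, and the section would continue the trial with the comparator and placebo, naming the same arm twice. Only the lower-case reading makes sense: b) is 1200.

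**2. The sections side by side, 600 failing alone.**

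| Section | Outcome |
|---|---|
| Step 1, Safety analysis | 600 closes; placebo and 1200 continue |
| Procedure for the conclusion | Not written; early conclusion is allowed for events in one group |
| End of Study | Step 1 stop does not apply (needs both arms) |

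**3. The plan's own figure.** Step 1 states a type I error of 10% and power of 80% for passing with 4 or fewer of 20. Exact binomial: P(X ≤ 4 | 20, 0.30) = 0.2375 and P(X ≤ 4 | 20, 0.05) = 0.9974. The stated values are not reproduced; 3 or fewer gives 0.1071 and 0.9841. This is a separate defect on which the present point does not depend. It does mean that a pass on 20 patients is weak reassurance, since an arm with a true 30% rate passes 23.75% of the time.

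**4. Probability that 600 closes and 1200 passes.** Inputs: n = 20 per arm and the cut-off of 4 (Step 1). Assumptions: independent arms, at most one SADR counted per patient, and true rates as shown; only 5% and 30% come from the protocol.

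P = P(X600 ≥ 5) × P(X1200 ≤ 4)

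| True rate 600 / 1200 | Calculation | Result |
|---|---|---|
| 5% / 5% | 0.0026 × 0.9974 | 0.3% |
| 10% / 10% | 0.0432 × 0.9568 | 4.1% |
| 15% / 15% | 0.1702 × 0.8298 | 14.1% |
| 20% / 20% | 0.3704 × 0.6296 | 23.3% |
| 30% / 30% | 0.7625 × 0.2375 | 18.1% |
| 5% / 10% | 0.0026 × 0.9568 | 0.2% |
| 10% / 20% | 0.0432 × 0.6296 | 2.7% |
| 20% / 30% | 0.3704 × 0.2375 | 8.8% |
| 30% / 40% | 0.7625 × 0.0510 | 3.9% |

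The Primary outcomes section uses a different limit: efficacy outcomes "will be measured only if the number of SADR is less than 4 in at least one of the treatment arms". With 3 or fewer as the pass limit, the equal-rate figures at 5, 10, 15, 20 and 30% are 1.6%, 11.5%, 22.8%, 24.2% and 9.6%.

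**5. Further evaluable patients on 1200 after Step 1.**
- Each arm goes to 34: 34 − 20 = 14.
- Total of 84 (Step 2, one experimental arm), with the closed arm's 20 counted: (84 − 20)/2 − 20 = 12.
- Total of 84, closed arm not counted: 84/2 − 20 = 22.

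**6. Peak concentration ratio, 1200 to 600.** 230/119 = 1.93 and 230/105 = 2.19. The numerator is a simulation; the denominators were measured in another study.

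**7. Worst-case cost of a pause**, if the review never released 1200. P(1200 goes on) falls from P(X1200 ≤ 4) to P(X1200 ≤ 4) × P(X600 ≤ 4):
- 5%/5%: 99.7% to 99.5%
- 10%/10%: 95.7% to 91.6%
- 15%/15%: 83.0% to 68.9%
- 20%/20%: 63.0% to 39.6%

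**The case against.** **Step 1 is explicit and complete.** It covers one arm failing and both failing, and the End of Study section agrees with it on the both-arms stop. The concluding section has a different, unquantified trigger and gives one example. A reader might infer that events confined to 600 end the trial there, in flat contradiction to Step 1. The documents do not establish that: it is drawn from silence. What stands is that the 600-only case is missing and that the general sentence, which allows conclusion for events in one group, sits awkwardly with Step 1.

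**The evidence that 1200 is more toxic is limited.** The Rationale reports that plasma levels of 248 and 260 ng/mL were well tolerated, cites a meta-analysis finding no difference in adverse-event severity between standard and higher doses, and says that both doses lie well below the maximum found safe. Appendix 1 says only that high concentrations can underlie adverse events, as the reason for an exploratory study. A reader might infer that the protocol itself holds 1200 to be the more dangerous dose; it does not. But none of this makes 1200 safer than 600, and a failure of 600 would itself call the tolerability argument into question.

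**Oversight exists outside Step 1.** SAEs reach the sponsor within 24 hours, pharmacovigilance staff may break the code for suspected unexpected serious reactions, SUSARs go to the authorities, the coordinating ethics committee and investigators, and urgent safety amendments can be made at once. So it would be wrong to infer that nobody would see the reactions on 600. None of these provisions, however, requires a decision about 1200 when 600 closes.

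**The outcome is improbable where the worry is greatest.** If 1200 is more toxic, it usually fails too. The largest figures need equal rates well above the planning rate, where the reversal is sampling noise. This stands, and it limits the weight of the point.

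**A pooled count would not guide the review.** With 5 events in 40 the probability of so few at a 30% rate is 0.009; with 9 in 40 it is about 0.20. Both totals can occur in this branch. This stands, and no pooled test is proposed.

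**Conclusion.** The point holds as a modest, inexpensive safety improvement. Step 1 continues the doubled dose automatically when the lower dose alone fails, and no other section requires 1200 to be looked at again or says clearly what happens. It is not an error in the sample size, alpha or power, and the pause is a design recommendation that the protocol does not itself imply.

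The outcome is negligible at the planning rate (0.3%) and uncommon if 1200 is the more toxic dose (0.2% to 8.8% over the pairs from 5%/10% to 30%/40%). It becomes material if the drug is more toxic than planned at both doses: 4.1% at 10% and 14.1% at 15%. These figures rest on independent arms, one SADR counted per patient, the Step 1 cut-off of 4, and assumed true rates.

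**What to change.** - **Step 1, Safety analysis.** Limit automatic continuation to the case where the closed arm is 1200. If 600 reaches 5 SADRs and 1200 does not, pause allocation to 1200 at once. The sponsor's existing safety and pharmacovigilance staff, with the coordinating investigator, review the SADRs of both ivermectin arms and document a decision to resume or stop. Use no pooled test against 30%. If 1200 is not released, the study stops as it would if both arms had failed.
- **Procedure for the conclusion of the trial.** Replace a) and b) with the doses and add the 600-only case.
- **End of Study.** Add the same stop.

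The cost is protocol wording, a pause as rare as the probabilities above, and some judgement in place of a fixed rule. The real downside is possible loss of the 1200 arm. The worst-case figures under step 7 of the working bound that loss: it is trivial at 5% in both arms but substantial at 20%. The actual loss would be smaller, since the review can release the arm.
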